**Table 7-2: Schedule of Assessments for Part B (MAD)**

Assessments	Screening Period (V1)	Confinement Days (V2)								Follow-up Visit (V3) Day 14 (±1 day)
	Day -28 to Day -2	-1	1 	2	3	4	5	6	7	
Informed Consent	X									
Randomization and Study Drug Administration 			X	X	X	X	X	X	X	
Inclusion/Exclusion Criteria	X	X								
Demography	X									
Medical/Medication History	X									
Assessment of AEs	X	X	X	X	X	X	X	X	X	X
Concomitant Medications	X	X	X	X	X	X	X	X	X	X
Vital Signs 	X	X	X	X	X	X	X	X	X	X
12-lead ECG 	X	X	X			X			X	X
Physical Examination	X	X							X	X
Height, Weight, BMI 	X									
Serology 	X									
Drug/Alcohol/Cotinine Screen	X	X								
Safety Laboratory: Hematology, Serum Chemistry, Urinalysis 	X	X		X		X			X	X
Spine X-ray examination 	X									
Blood Pharmacokinetic Sampling 			X	X	X	X	X	X	X	
CSF Pharmacokinetic Sampling 			X						X	
CSF Pharmacodynamic Sampling 			X						X	
Plasma Pharmacodynamic Sampling 			X						X	
Scales 		X	X	X					X	X
C-SSRS 	X				X				X	

AE: adverse event; BMI: body mass index; BP: blood pressure; CSF: Cerebrospinal fluid; C-SSRS: Columbia Suicide Severity Rating Scale; K-WAIS-IV: Korean Wechsler Adult Intelligence Scale-IV; ECG: electrocardiogram; ED: Early Discontinuation; HCV: hepatitis C virus; HBsAg: hepatitis B surface antigen; HAV: hepatitis A virus; HIV: human immunodeficiency virus; VAS: Visual Analogue Scale; POMS: Profile of Mood States

1. On Day 1, any predose procedures should be performed within 2 hour before study drug administration.
2. Discharge assessments to be performed for ED.
3. Randomization occurs on Day 1 prior to dosing.
4. Vital signs include tympanic temperature, supine pulse, and supine BP. Vital signs will be collected after the subject has been in a supine position for at least 5 minutes. On Day 1 and Day 4, vital signs will be measured at predose and at 1 hour postdose; On Day 2, Day 3, Day 5, Day 6, and Day 7, vital signs will be measured at predose. Timing of vital signs measurements may be shifted and/or added based on the results of Part A.
5. 12-lead ECGs will be obtained in triplicate within 5 minutes, with at least a 1-minute interval. On Day 1 and Day 4, ECGs will be recorded at predose and at 1 hour postdose. ECGs should be performed prior to pharmacokinetic and safety laboratory blood draws.
6. Screening height and weight will be used for BMI calculation for assessment of eligibility.
7. Blood will be tested for HBsAg, anti-HAV IgM, anti-HCV Ab, and anti-HIV Ab.
8. All hematology and serum chemistry labs will be taken after fasting for a minimum of 8 hours.
9. Simple spine X-ray examination will only be conducted at Screening for healthy elderly cohort.
10. Plasma samples for pharmacokinetics of KM-819 will be obtained on Day 1 predose (within 30 minutes prior to study drug administration) and 0.25, 0.5, 1, 2, 4, 6, 8, and 12 hours postdose, predose on Days 2, 3, 4, 5, 6,

---

and on Day 7 predose (within 30 minutes prior to study drug administration) and 0.25, 0.5, 1, 2, 4, 6, 8, 12, and 24 hours postdose.

11. CSF samples for pharmacokinetic of KM-819 will be obtained on Day 1 (at -120 minutes to 0 minute prior to the first dosing) and on Day 7 (at 1 hour after last dosing).
12. CSF samples for pharmacodynamic of KM-819 will be obtained on Day 1 (at -120 minutes to 0 minute prior to the first dosing) and on Day 7 (at 1 hour after last dosing).
13. Plasma samples for pharmacodynamic of KM-819 will be obtained on Day 1 (within 30 minutes prior to study drug administration) and on Day 7 (at 1 hour after last dosing).
14. Bond and Lader VAS, POMS, and K-WAIS-IV will be performed on Day -1, on Day 1 and Day 7 at predose, 3, 6, 12, and 24 hours postdose ( $\pm$  30 minutes for each time point).
15. The version of the C-SSRS to be performed at Screening is the “Baseline-Screening for Phase 1,” and the version of the C-SSRS to be performed on Day 3 and Day 8 (or at ED) is the “Since Last Visit”.

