#### *1.2.1.3 Pharmacokinetics*

A pharmacokinetic (PK) study in male rats, by administering single intravenous (IV) injection of 5 mg/kg KM-819 showed:  $C_{max}$ : 62.73 ug/ml,  $t_{max}$ : 0.083 hr, and  $t_{1/2}$ : 7.08 hr. Single dose oral administration of 5 mg/kg KM-819 resulted in:  $C_{max}$ : 3.89 ug/ml,  $t_{max}$ : 3 hr, and  $t_{1/2}$ : 6.06 hr. Oral bioavailability assessed by comparing  $AUC_{0-\infty}$  for oral and IV administration was 35.97%.

A PK study in male dogs, by administering single IV injection of 1 mg/kg KM-819 showed:  $t_{max}$ : 0.08 hr,  $C_{max}$ : 11.91 ug/ml, and  $t_{1/2}$ : 8.61 hr. Single dose oral administration of 5 mg/kg and 10 mg/kg KM-819 resulted in:  $t_{max}$ : 0.83 hr and 0.58 hr,  $C_{max}$ : 6.01 ug/ml and 9.48 ug/ml, and  $t_{1/2}$ : 4.96 hr and 5.03 hr, bioavailability: 32.3% and 28.9%, respectively.

In vitro plasma protein binding is 99.96 %, 99.79%, and 99.96% in rat, dog and human, respectively. KM-819 at 10 uM did not inhibit CYP450s (including 1A2, 2C9, 2C19, 2D6, 3A4) and P-gp.

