**Figure 3-1: Part A Single Ascending Dose Study Design**

**Part B, Multiple Ascending Dose (MAD)**

Part B will be conducted after completion of all cohorts of young adult male subjects in Part A. Up to 32 healthy young adult male subjects and 8 healthy elderly male or post-menopausal female subjects will be enrolled and randomized to receive either KM-819 or placebo.

Each of the 4 dose escalation cohorts will consist of 8 healthy young adult male subjects; 6 subjects will receive 30, 100, 200, or 400 mg of KM-819 once a day (QD) for 7 days and 2 subjects will receive placebo. Cohorts will be dosed sequentially with escalating doses.

After completion of the 4 dose escalation cohorts, 8 elderly male or post-menopausal female subjects will be enrolled into an additional cohort; 6 subjects will receive 200 mg KM-819 QD for 7 days and 2 subjects will receive placebo.

[figure not shown]
See Table 3-2 for Part B dose groups.

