## 7 STUDY CONDUCT

### 7.1 Schedule of Procedures

**Table 7-1: Schedule of Assessments for Part A (SAD)**

Assessments	Screening Period (V1)	Confinement Days (V2)				Outpatient Visit Day (V3-V4)		Follow-up Visit (V5)
	Day -28 to Day -2	-1	1 	2	3 	Day 4	Day 7	Day 14 (±1 day)
Informed Consent	X							
Randomization and Study Drug Administration 			X					
Inclusion/Exclusion Criteria	X	X 						
Demography	X							
Medical/Medication History	X							
Assessment of AEs	X	X	X	X	X	X	X	X
Concomitant Medications	X	X	X	X	X	X	X	X
Vital Signs 	X	X	X	X	X	X	X	X
12-lead ECG 	X	X	X	X			X	X
Physical Examination	X	X			X	X	X	X
Height, Weight, BMI 	X							
Serology 	X							
Drug/Alcohol/Cotinine Screen	X	X						
Safety laboratory: Hematology, Serum Chemistry, Urinalysis 	X	X		X			X	X
Blood Pharmacokinetic Sampling 			X	X	X	X		
Urine Sampling 				X	X			
Scales 			X	X	X	X		
C-SSRS 	X				X			

AE: adverse event; BMI: body mass index; BP: blood pressure; C-SSRS: Columbia Suicide Severity Rating Scale; K-WAIS-IV: Korean Wechsler Adult Intelligence Scale-IV; ECG: electrocardiogram;

ED: Early Discontinuation; HCV: hepatitis C virus; HBsAg: hepatitis B surface antigen; HAV: hepatitis A virus; HIV: human immunodeficiency virus; VAS: Visual Analogue Scale; POMS: Profile of Mood States

1. On Day 1, any predose procedures should be performed within 2 hour before study drug administration.
2. Discharge assessments to be performed for ED are the Day 3 assessments supplemented with an ECG and safety labs, see Section 7.2.4.
3. Randomization occurs on Day 1 prior to dosing.
4. Confirmation of inclusion and exclusion criteria.
5. Vital signs include tympanic temperature, supine pulse and supine BP. Vital signs will be collected after the subject has been in a supine position for at least 5 minutes. On Day 1, vital signs will be measured at predose, and at 0.5, 1, 2, and 4 hour postdose.
6. 12-lead ECGs will be obtained in triplicate within 5 minutes, with at least a 1-minute interval. On Day 1, ECGs will be recorded at predose and at 1 hour postdose. ECGs should be performed prior to pharmacokinetic and safety laboratory blood draws.
7. Screening height and weight will be used for BMI calculation for assessment of eligibility.
8. Blood will be tested for HBsAg, anti-HAV IgM, anti-HCV Ab, and anti-HIV Ab.

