9. All hematology and serum chemistry labs will be taken after fasting for a minimum of 8 hours.
10. Plasma samples for pharmacokinetics of KM-819 will be obtained on Day 1 predose (within 30 minutes prior

---

to study drug administration) and 0.25, 0.5, 1, 2, 4, 6, 8, 12, 24, 48, and 72 hours postdose.

11. Urine samples will be taken at: Day 1 predose (within 1 hour before study drug administration) and from 0 to 24 hours postdose.
12. Bond and Lader VAS, POMS, and K-WAIS-IV will be performed on Day -1, Day 1 (predose) and at 3, 6, 12, 24, 48, and 72 hours postdose ( $\pm$  30 minutes for each time point).
13. The version of the C-SSRS to be performed at Screening is the “Baseline-Screening for Phase 1,” and the version of the C-SSRS to be performed on Day 3 (or at ED) is the “Since Last Visit”.

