### ***7.2.3 Visits for Part B Multiple Ascending Dose***

#### *7.2.3.1 Confinement Visit (Visit 2)*

Visit 2 for MAD will occur within 28 days after Screening.

On Day -1 (check-in), subjects will need to attend the study center, the following assessments will be performed:

- confirmation of inclusion/exclusion criteria
- concomitant medication
- assessment of AE
- vital signs measurement and physical examination
- ECG assessment
- hematology and biochemistry blood sampling
- urinalysis sampling
- urine drug/cotinine tests
- alcohol breath test

- scales assessment

All results necessary for evaluation of the inclusion and exclusion criteria must be available before determining whether or not the subject can continue in the study.

Once verified eligible to the study, the subjects will be required to stay in study center for 8 nights (confined from the evening of Day -1 to Day 8).

On Day 1, the procedures to be performed at predose are listed below:

- Randomization: eligible subjects will be randomized to receive either KM-819 or placebo
- vital signs measurement (predose)
- ECG assessment (predose)
- scales assessments (predose)
- CSF PK and PD sampling (at -120 minutes to 0 minutes before dosing)
- PK blood sampling within 30 minutes before dosing
- plasma PD sampling within 30 minutes before dosing

Study drug will be administered from 8:00 to 10:00.

The procedures to be performed at postdose are listed below:

- postdose PK blood sampling at 0.25, 0.5, 1, 2, 4, 6, 8, and 12 hours (see Table 7-2)
- postdose vital signs measurements at 1 hour
- postdose ECG assessment at 1 hour
- postdose scales assessments at 3, 6, and 12 hours

The following assessments will also be performed during Day 1:

- concomitant medication
- assessment of AE

On Day 2 to Day 6, the procedures to be performed on each day are listed below:

- concomitant medication
- assessment of AE
- vital signs measurement (at predose and at 1 hour postdose on Day 4; at predose on Day 2, Day 3, Day 5, and Day 6)
- ECG assessment (at predose and at 1 hour postdose on Day 4)
- hematology and biochemistry blood sampling (only on Day 2 and Day 4)
- urinalysis sampling (only on Day 2 and Day 4)
- PK blood sampling within 30 minutes before each dosing
- study drug administration from 8:00 to 10:00
- scales assessments at 24 hours after first dosing (only on Day 2)
- C-SSRS assessment (only on Day 3)

On Day 7, the procedures to be performed before last dose are listed below:

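### Part B fixes its only ECGs within 12 hours after a dose at 1 hour and, unlike vital signs, cannot move them to the tmax that Part A will have shown

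*Protocol*

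**What the plan says.** Protocol Section 3.2.1 names 12-lead ECG as one of four groups of safety endpoints.

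**Part B ECG times.** Table 7-2 footnote 5 reads: "On Day 1 and Day 4, ECGs will be recorded at predose and at 1 hour postdose". Section 7.2.3.1 agrees, listing "postdose ECG assessment at 1 hour" on Day 1 and "ECG assessment (at predose and at 1 hour postdose on Day 4" for the later dosing days. It lists no ECG on Day 7 and places the next one on Day 8, when the 24-hour PK sample after the last dose is due. The on-treatment ECGs in Part B are therefore 1 h after dose 1, a Day 4 predose trough, 1 h after dose 4, and 24 h after dose 7.

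**Vital signs.** These share the predose and 1-hour times on Days 1 and 4, but footnote 4 adds: "Timing of vital signs measurements may be shifted and/or added based on the results of Part A". No equivalent sentence for the ECG appears in footnote 5, in Section 6.4.4 or in the SAP.

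**What is known before Part B.** Section 3.1 states: "Part B will be conducted after completion of all cohorts of young adult male subjects in Part A". Those cohorts are sampled at "0.25, 0.5, 1, 2, 4, 6, 8, 12, 24, 48, and 72 hours postdose" (Table 7-1), and tmax is a listed PK parameter. Five cohorts of six active subjects give up to 30 profiles.

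**Part A ECG.** Table 7-1 has the same restriction: "On Day 1, ECGs will be recorded at predose and at 1 hour postdose".

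**The concern.** One hour was chosen before any human PK existed. Section 5.3 predicts clearance, volume and half-life but gives no absorption rate and no tmax. The only tmax evidence is from animals (Section 1.2.1.3), and it spans about five-fold after oral dosing: 0.83 h and 0.58 h in dogs, against 3 h in rats, where "Single dose oral administration of 5 mg/kg KM-819 resulted in" the later peak. One hour suits the dog values but not the rat value.

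Footnote 4 shows that the sponsor foresaw that post-dose times might need to follow Part A, yet it covers only one of two assessments taken at the same clock times. Section 9.8 requires the protocol to be followed as written, with non-administrative changes going through amendment, so nothing moves the ECG by default.

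If human tmax turns out late, the ECG summaries at each repeated dose would describe concentrations below the peak which that dose produces. Part A would not fill the gap, because its Day 1 post-dose ECG is also at 1 h.

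**Working it through.** **Inputs.** CL = 2.93 L/h, V = 39.2 L, and a one-compartment model with first-order absorption and elimination (Section 5.3). Dosing interval 24 h (Part B). Animal oral tmax 0.58, 0.83 and 3 h (Section 1.2.1.3). Human tmax is not given, so it is assumed and varied; no lag time is assumed.

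**Step 1: reproduce the plan's figure.** k = CL/V = 2.93/39.2 = 0.0747 per h. Half-life = ln 2 / k = 0.6931 × 39.2/2.93 = 9.27 h, as the protocol states.

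**Step 2: absorption rate for each assumed tmax.** Solve tmax = ln(ka/k)/(ka − k) for ka. For tmax = 3 h, ka = 0.907 per h.

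**Step 3: share of Cmax at 1 h after dose 1.** C(t) is proportional to exp(−kt) − exp(−ka·t); dose and bioavailability cancel in the ratio. For tmax = 3 h:
- at 1 h: 0.928 − 0.404 = 0.524
- at 3 h: 0.799 − 0.066 = 0.733
- ratio: 0.524/0.733 = 0.715

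**Step 4: the same after dose 4, by superposition.** The elimination term is multiplied by (1 − exp(−96k))/(1 − exp(−24k)) = 0.9992 × 1.1995 = 1.199. For tmax = 3 h the absorption terms from earlier doses are negligible and the dose 4 peak falls at 2.78 h:
- at 1 h: 0.928 × 1.199 − 0.404 = 0.709
- at 2.78 h: 0.812 × 1.199 − 0.080 = 0.893
- ratio: 0.709/0.893 = 0.79

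**Results: C(1 h) as a share of Cmax**

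| Assumed single-dose tmax | After dose 1 | After dose 4 |
|---|---|---|
| 0.58 h (dog, 10 mg/kg) | 98% | 98% |
| 0.83 h (dog, 5 mg/kg) | 100% | 99% |
| 1 h | 100% | 100% |
| 1.5 h | 97% | 98% |
| 2 h | 89% | 92% |
| 3 h (rat, 5 mg/kg) | 71.5% | 79% |

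**Step 5: is Day 4 the weak point, or the hour?** The share of steady state reached after four doses is 1 − exp(−96k) = 99.9%. Under the predicted half-life Day 4 is late enough; the hour is what matters.

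**Step 6: what a movable time would recover.** If tmax is 3 h, the two neighbouring PK times give, after dose 1:
- 2 h: (0.861 − 0.163)/0.733 = 95%
- 4 h: (0.742 − 0.027)/0.733 = 98%

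Either compares with 71.5% at 1 h.

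**The case against.** The strongest case against is that the loss depends on a number the documents do not contain. At both dog values, and up to about 1.5 h, the 1-hour ECG catches at least 97% of Cmax. That stands: this is a conditional weakness, not a demonstrated miss.

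The protocol also reports no hERG inhibition up to 10 uM and no heart-rate, blood-pressure or ECG change, QT included, in male dogs up to 500 mg/kg (Section 1.2.1.2). Subjects with raised QTcF or a relevant cardiac history are excluded. A sparse ECG schedule is defensible on that footing. This lowers the prior concern but does not show when human exposure peaks.

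A sub-peak ECG at the top dose still carries information. In the rat-like case, and if exposure is dose-proportional, the Day 4 ECG at 400 mg would sit at about 2 × 0.79 = 1.6 times the 200 mg peak.

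There are other routes too. The investigator and sponsor review safety and PK after each cohort, unscheduled ECGs would be listed, and the protocol can be amended. None of these is a planned adjustment of ECG timing.

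A reader might go further in two ways that the documents do not support:
- **Larger losses.** The same model gives 58% of Cmax on Day 1 at a tmax of 4 h and 41% at 6 h. No tmax in the documents exceeds 3 h. Lag time is only a listed PK parameter; no lag is reported.
- **An unsafe claim of no ECG effect, or a compromised primary objective.** No such claim is planned. ECG analysis is listings and descriptive statistics (protocol Section 8.6.2, SAP Section 6.3.15.4), with no QTc margin, test or concentration-QT model. One time point of one of four safety endpoint groups is not the primary objective.

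**Conclusion.** The point holds as a cheap improvement in assessment timing. Part B's only ECGs within 12 h after a dose are fixed at 1 h, while the information needed to place them better will exist before Part B starts and is already allowed to guide vital signs.

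Over the documents' own tmax range of 0.58 to 3 h, the shortfall from Cmax at the ECG is 0% to 29% on Day 1 and 0% to 21% on Day 4. It becomes material only if human tmax is later than about 1.5 to 2 h; the descriptive ECG summaries would then reflect sub-peak exposure.

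These figures rest on the predicted CL and V, the one-compartment model, no lag time, and animal tmax as the plausible human range. The documents do not show that the peak will be missed.

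**What to change.** Extend the footnote 4 provision to Table 7-2 footnote 5, with matching text in Section 7.2.3.1. The single post-dose triplicate ECG on Day 1 and Day 4 is taken at the scheduled Day 1 PK sampling time nearest the median tmax. The median is pooled over all active young adult Part A subjects and doses, and 1 h is kept if it is nearest. The elderly Part A cohort is left out because Part B does not wait for it. State in advance which time is used if the median falls midway between two sampling times, as 3 h would between 2 h and 4 h.

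The number of ECGs is unchanged and no PK sample is added; Day 4 has only a predose sample, so its ECG would use the same clock time without a paired concentration.

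Costs and limits:
- The post-dose ECG time may differ between Parts A and B.
- Section 5.2 withholds food for at least 4 h after the Day 1 dose but at least 2 h on Days 2 to 6. An ECG later than 2 h could be fasted on Day 1 and fed on Day 4, which should be noted when the ECG data are interpreted.
- One post-dose time still leaves subjects whose tmax is far from the median uncovered.

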**Table 7-3: Pharmacokinetic Sampling Time points for Part A (SAD)**

Visits	Nominal time		Remark
	Sampling time	Sampling windows	
Visit 2, Day 1	Predose	- 30 min	Baseline sample
			Study drug administration
	0.25 hour	+ 2 min	
	0.5 hour	± 3 min	
	1 hour	± 5 min	
	2 hour	± 10 min	
	4 hour	± 10 min	
	6 hour	± 10 min	
	8 hour	± 10 min	
	12 hour	± 15 min	
Visit 2, Day 2	24 hour	± 15 min	
Visit 2, Day 3	48 hour	± 60 min	
Visit 3, Day 4	72 hour	± 60 min	

**Table 7-4: Pharmacokinetic Sampling Time points for Part B (MAD)**

Visits	Nominal time		Remark
	Sampling time	Sample windows	
Visit 2, Day 1	Predose	- 30 min	Baseline sample
			First study drug administration
	0.25 hour	+ 2 min	
	0.5 hour	± 3 min	
	1 hour	± 5 min	
	2 hour	± 10 min	
	4 hour	± 10 min	
	6 hour	± 10 min	
	8 hour	± 10 min	
	12 hour	± 15 min	
Visit 2, Day 2	Predose	- 30 min	24 hour after first dose
Visit 2, Day 3	Predose	- 30 min	Trough sample
Visit 2, Day 4	Predose	- 30 min	Trough sample
Visit 2, Day 5	Predose	- 30 min	Trough sample
Visit 2, Day 6	Predose	- 30 min	Trough sample
Visit 2, Day 7	Predose	- 30 min	Predose sample
			Last study drug administration
	0.25 hour	+ 2 min	
	0.5 hour	± 3 min	
	1 hour	± 5 min	
	2 hour	± 10 min	
	4 hour	± 10 min	
	6 hour	± 10 min	
	8 hour	± 10 min	
	12 hour	± 15 min	
Visit 2, Day 8	24 hour	± 15 min	

## 7.2 Procedures by Visit

Visits should occur within visit windows (defined in Table 7-1 and Table 7-2) of the scheduled visits. All times should be recorded using the 24-hour clock (e.g., 23:20, not 11:20 pm).

### 7.2.1 Screening (Visit 1) for Part A and Part B

The subjects will receive verbal and written information about the study and the procedures involved before Screening. Before any study-related activities are performed, the subject must have given written informed consent to study participation.

The Screening Period may extend up to 27 days from the time the informed consent form (ICF) is signed. The subject may visit the site more than one time during this period.

The assessments to be performed at this visit are listed below:

- inclusion/exclusion criteria assessment
- demographic and medical/medication history data collection
- concomitant medication
- assessment of AE
- vital signs measurement and physical examination
- ECG assessment
- body measurements (weight, height, and BMI)
- hematology and biochemistry blood sampling
- serology blood sampling
- urinalysis sampling
- urine drug/cotinine tests
- alcohol breath test
- C-SSRS assessment
- spine X-ray examination (only for healthy elderly cohort in Part B)

### 7.2.2 Visits for Part A Single Ascending Dose

#### 7.2.2.1 Confinement Visit (Visit 2)

Visit 2 for SAD will occur within 28 days after Screening.

On Day -1 (check-in), subjects will need to attend the study center, the following assessments will be performed:

- confirmation of inclusion/exclusion criteria
- concomitant medication
- assessment of AE
- vital signs measurement and physical examination
- ECG assessment
- hematology and biochemistry blood sampling
- urinalysis sampling

- urine drug/cotinine tests
- alcohol breath test
- scales assessment

All results necessary for evaluation of the inclusion and exclusion criteria must be available before determining whether or not the subject can continue in the study.

Once verified eligible to the study, the subjects will be required to stay in study center for 3 nights (confined from the evening of Day -1 to Day 3).

On Day 1, the procedures to be performed at predose are listed below:

- Randomization: eligible subjects will be randomized to receive either KM-819 or placebo
- vital signs measurement (predose)
- ECG assessment (predose)
- scales assessments (predose)
- Urine sampling within 1 hour before dosing
- PK blood sampling within 30 minutes before dosing

Study drug will be administered from 8:00 to 10:00.

The procedures to be performed at postdose are listed below:

- postdose PK blood sampling at 0.25, 0.5, 1, 2, 4, 6, 8, and 12 hours (see Table [7-1](#))
- postdose vital signs measurements at 0.5, 1, 2, and 4 hours
- postdose ECG assessment at 1 hour
- postdose urine sampling from 0 to 24 hours
- postdose scales assessments at 3, 6, and 12 hours

The following assessments will also be performed during Day 1:

- concomitant medication
- assessment of AE

On Day 2 to Day 3, the procedures to be performed are listed below:

- concomitant medication
- assessment of AE
- vital signs measurement
- ECG assessment (only on Day 2)
- hematology and biochemistry blood sampling (only on Day 2)
- urinalysis sampling (only on Day 2)
- postdose PK blood sampling at 24 hour and 48 hours
- postdose scales assessments at 24 hours and 48 hours
- physical examination (only on Day 3)
- C-SSRS assessment (only on Day 3)

Subjects will be allowed to leave the study center after completing all the procedures on Day 3.

